### 9.4 Statistical Analyses

The SAP will be developed and finalized before database lock and will describe the patient populations to be included in the analyses, and procedures for accounting for missing, unused, and spurious data. This section is a summary of the planned statistical analyses of the primary and secondary endpoints.

#### 9.4.1 Efficacy Analyses

The primary efficacy analyses (Table 11) will be performed on the efficacy population. Efficacy analyses based on the response-evaluable population may be performed as a sensitivity analysis. Details of the censoring scheme on time-to-event endpoints such as DOR and PFS will be described in the SAP.

**Table 11: Efficacy – Statistical Analyses**

Endpoint	Statistical Analysis Methods
ORR is defined as the proportion of patients whose BOR is either confirmed CR or PR per RECIST v1.1 in the population of interest.	Estimate of ORR and corresponding 2-sided exact 90% CI using the Clopper-Pearson method
BOR for a patient will be assessed per RECIST v1.1 by the investigator, unless otherwise specified.	Estimate of DCR and corresponding 2-sided exact 90% CI using the Clopper-Pearson method
DCR defined as total number of patients with confirmed responses of either CR, PR, or stable disease as determined by the investigator per RECIST v1.1, divided by the total number of patients who are evaluable for a response	
DOR DOR for a patient with a BOR of confirmed CR or PR is defined as the time between the date of first response and the date of the first objectively documented tumor progression per RECIST v1.1 or death, whichever occurs first.	Estimate by the Kaplan-Meier method and corresponding 2-sided 90% CI using Brookmeyer and Crowley methodology (using log-log transformation)
PFS PFS for a patient is defined as the time from the first dosing date to the date of first objectively documented disease progression or death due to any cause, whichever occurs first.	Estimate by the Kaplan-Meier method and corresponding 2-sided 90% CI using Brookmeyer and Crowley methodology (using log-log transformation)
OS OS for a patient is defined as the time from the first dose of study treatment until death from any cause.	Estimate by the Kaplan-Meier method and corresponding 2-sided 90% CI using Brookmeyer and Crowley methodology (using log-log transformation)

Abbreviations: BOR = best overall response; CI = confidence interval; CR = complete response; DOR = duration of response; DCR= disease control rate; PFS = progression free survival; OS = overall survival; PR = partial response; RECIST v1.1 = Response Evaluation Criteria in Solid Tumors version 1.1.

#### 9.4.2 Safety Analyses

All safety analyses will be performed on the Safety Population.

Safety analyses will be performed separately within both phases of the study and for all patients combined. In addition, the incidence of DLTs in Phase 1a will be summarized for the DLT-Evaluable Population.

**Table 12: Safety – Statistical Analyses**

Endpoint	Statistical Analysis Methods
Incidence of DLTs, AEs, SAEs, and AEs leading to discontinuation, modifications, and interruptions, and death  AEs will be graded according to CTCAE v4.03.	Frequency distribution of treated patients with AE using the worst CTC grade. Patients will only be counted (1) once at the preferred term level, (2) once at the SOC level, and (3) once in the “Total subject” row at their worst CTC grade, regardless of SOC or preferred term.
Laboratory abnormalities  Laboratory values will be graded according to CTCAE v4.03.	Laboratory shift table using the worst CTC grade on treatment per patient.
ECG abnormality	Frequency distribution of treated patients with post baseline ECG abnormality by visit.

Abbreviations: AE = adverse event; CTCAE = common terminology criteria for adverse events; DLT = dose limiting toxicity; ECG = electrocardiogram; SOC = system organ class.

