### 3.0 OBJECTIVES AND ENDPOINTS

#### Objectives and Endpoints – Phase 1a Dose Escalation/Exploration – FPT155 Monotherapy:

Objectives	Endpoints
Primary	
Safety 
 
• To assess the safety and tolerability of FPT155 as monotherapy in patients with advanced solid tumors
 
• To determine the RD of FPT155 as monotherapy
 
	Safety 
 
• The incidence of adverse events (AEs), serious adverse events (SAEs), clinical laboratory abnormalities, and electrocardiogram (ECG) abnormalities
 
• The incidence of AEs defined as dose limiting toxicities (DLTs), clinical laboratory abnormalities defined as DLTs, and overall assessment of pharmacokinetics (PK) and pharmacodynamics (PD)
 

Secondary	
Pharmacokinetics 
 
• To characterize the PK profile of FPT155 as monotherapy in patients with advanced solid tumors
 
	Pharmacokinetics The following PK parameters will be derived from concentration-time data for FPT155 when appropriate and applicable. 
 
• Area under serum concentration-time curve (AUC)
 
• Maximum observed serum concentration (<math>C_{max}</math>)
 
• Trough observed serum concentration at the end of each dose interval (<math>C_{trough}</math>)
 
• Clearance (CL)
 
• Terminal half-life (<math>t_{1/2}</math>)
 
• Volume of distribution at steady state (<math>V_{ss}</math>)
 
 Other parameters, such as dose proportionality, accumulation ratio, and attainment of steady state, will also be calculated if the data are available.
Immunogenicity 
 
• To characterize the immunogenicity of FPT155 as monotherapy in patients with advanced solid tumors
 
	Immunogenicity 
 
• Incidence of treatment emergent anti-FPT155 antibody response
 

Exploratory	

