### Objectives and Endpoints – Phase 1b Dose Expansion – FPT155 Monotherapy:

Objectives	Endpoints
Primary	
Safety 
 
To evaluate the safety and tolerability of FPT155 as monotherapy in patients with selected advanced solid tumors treated at the RD
 
	Safety 
 
The incidence of AEs, SAEs, clinical laboratory abnormalities, and ECG abnormalities
 
The incidence of treatment discontinuations, modifications, and interruptions due to AEs
 

Secondary	
Efficacy 
 
To evaluate the clinical benefit of FPT155 as monotherapy in patients with selected advanced solid tumors treated at the RD through the analysis of ORR, DOR, PFS, and DCR
 
	Efficacy 
 
ORR, DOR, and PFS
 
Disease Control Rate (DCR) defined as total number of patients with confirmed responses of either CR, PR, or stable disease as determined by the investigator per RECIST v1.1, divided by the total number of patients who are evaluable for a response
 

Objectives	Endpoints

Pharmacokinetics
 
 
• To characterize the PK profile of FPT155 as monotherapy in patients with selected advanced solid tumors treated at the RD
 
	
Pharmacokinetics
 
The following PK parameters will be derived from concentration-time data for FPT155 when appropriate and applicable.
 
 
• AUC
 
• <math>C_{max}</math>
 
• <math>C_{trough}</math>
 
• CL
 
• <math>t_{1/2}</math>
 
• <math>V_{ss}</math>
 
 
Other parameters, such as dose proportionality, accumulation ratio, attainment of steady state, will also be calculated if the data are available. Assessment of time-dependence of PK, the effect of body weight as well as other covariates on PK, and the exposure-response relationship, when the data allow, will be conducted to determine the appropriate dosing approach (eg, body weight-based or fixed dosing) for future trials.

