### **Other Exclusions**

3.01) Immunosuppressive doses of systemic medications, such as steroids or absorbed topical steroids (doses > 10 mg/day prednisone or equivalent daily) must be discontinued at least 2 weeks before study treatment administration

3.02) QTcF > 450 msec for males or > 470 msec for females at screening

3.03) Severe allergic, anaphylactic, or other infusion-related reaction to a previous biologic agent

3.04) Known history of sensitivity to infusions containing Tween 20 (polysorbate 20), L histidine, and sucrose

3.05) Vaccines (eg, human papillomavirus [HPV] vaccine) within 4 weeks of study treatment administration. The inactivated seasonal influenza vaccine can be given to patients before treatment and while on therapy without restriction. Influenza vaccines containing live virus or other clinically indicated vaccinations for infectious diseases (eg, pneumovax, varicella) may be permitted, but must be discussed with the Sponsor's medical monitor and may require a study treatment washout period prior to and after administration of vaccine

3.06) Patients with abnormal serum chemistry values that in the opinion of the investigator are considered to be clinically significant. This will include patients who show clinical signs and symptoms related to their abnormal serum chemistry values as well as patients whose serum chemistry values are asymptomatic but clinically significant per investigator (eg, hypokalemia or hyponatremia).

3.07) Pregnant or breastfeeding

3.08) Known history of testing positive for human immunodeficiency virus (HIV) 1 or 2 or known acquired immunodeficiency syndrome (AIDS)

- 3.09) Positive test for hepatitis B virus surface antigen (HBsAg) or detectable hepatitis C virus ribonucleic acid (HCV RNA) indicating acute or chronic infection
- 3.10) Transfusion of blood or platelets or granulocyte-colony stimulating factor (G-CSF) administration completed within 72 hours prior to first dose of study treatment

No waivers of these inclusion or exclusion criteria will be granted.

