5.4 Definition of Baseline

When appropriate, baseline is defined as the last non-missing result with a collection date-time less than the date-time of the first dose of study medication.

For continuous measurements before the first dose, if multiple measurements occur on the same day, the last non-missing value will be considered as the baseline value. If these multiple measurements occur at the same time, the last non-missing value will be used as baseline. For categorical measurements before the first dose, if multiple measurements occur on the same day, the last non-missing value will be considered as the baseline value. If these multiple measurements occur at the same time or the time is not available, the last non-missing value will be considered as the baseline value.

Measurements occurred after first dose date will be considered post baseline values.

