6.3 Safety Analyses

Safety analyses will be performed separately for Phase 1a Monotherapy Dose Escalation/Exploration, Phase 1b Monotherapy Dose Expansion, Phase 1a Combination Dose Escalation/Exploration and for all patients combined. AEs, clinical laboratory information, vital signs, ECOG performance status, weight, ECGs, and concomitant medications/procedures will be tabulated and summarized for the Safety Population. In addition, the incidence of DLTs in Phase 1a will be summarized using DLT-Evaluable Population. Unless otherwise specified, all analyses will be performed using the Safety Population.

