6.3.4 Vital Signs

Vital signs parameters including systolic blood pressure, diastolic blood pressure, pulse, respiration rate, and temperature will be summarized for absolute values and change from baseline by visit and time point for safety population. By-subject listing of vital signs and vital signs during infusion will be provided.

6.3.5 12-Lead ECG

A by-subject listing of 12-lead ECG abnormality (abnormal clinical significant, and abnormal not clinically significant) will be provided.

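### The ECG analysis is not referenced to the baseline ECG: Protocol Table 12 counts post-baseline abnormality by visit and SAP 6.3.5 gives only a listing, so neither yields the number of patients with a new or worsened ECG

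*Protocol*

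**What the plan says.** **Endpoint.** The Phase 1a monotherapy primary safety endpoint (Protocol Section 3.0) is "The incidence of adverse events (AEs), serious adverse events (SAEs), clinical laboratory abnormalities, and electrocardiogram (ECG) abnormalities". Phase 1b has the same content: "The incidence of AEs, SAEs, clinical laboratory abnormalities, and ECG abnormalities". The combination part repeats it.

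**Protocol analysis.** Table 12 (Section 9.4.2) gives one line for ECGs: "Frequency distribution of treated patients with post baseline ECG abnormality by visit". The laboratory row of the same table reads "Laboratory shift table using the worst CTC grade on treatment per patient", which by its nature uses the baseline grade.

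**SAP analysis.** Section 6.3 states: "AEs, clinical laboratory information, vital signs, ECOG performance status, weight, ECGs, and concomitant medications/procedures will be tabulated and summarized for the Safety Population". Section 6.3.5 (12-Lead ECG) then specifies only this: "A by-subject listing of 12-lead ECG abnormality (abnormal clinical significant, and abnormal not clinically significant) will be provided". Neither document specifies an ECG shift table, a change from baseline or a count of new cases.

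**Baseline.** SAP 5.4 supplies a usable definition: "baseline is defined as the last non-missing result with a collection date-time less than the date-time of the first dose of study medication". Screening and pre-dose Cycle 1 Day 1 ECGs are required in both schedules (Protocol Tables 1 and 2).

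**Eligibility.** The only ECG-based exclusion is criterion 3.02: "QTcF > 450 msec for males or > 470 msec for females at screening".

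**The concern.** An incidence endpoint should say how many patients developed something they did not have before treatment. The Table 12 row does not separate those patients from patients whose tracing was already abnormal. Such patients can enroll: apart from QTcF there is no ECG limit, and the SAP's own category of abnormal but not clinically significant tracings anticipates them.

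ECG is also the exception in this plan. Laboratory grades are shifted from baseline (SAP 6.3.3), vital signs are summarized as change from baseline (SAP 6.3.4), treatment-emergent events are defined against the pre-treatment state (SAP 6.3.1.5), and baseline-positive ADA is kept apart from treatment-induced ADA (SAP 6.4.3).

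At stake is whether the study report can state, for each dose and cohort, how many patients acquired or worsened an ECG abnormality. As written, the protocol table would mix old and new abnormalities, and the SAP would leave the reader to count from a listing.

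**Working it through.** The documents state no ECG rate, power or precision, so there is no planned figure to reproduce. All analyses are descriptive (Protocol Section 9.0). What follows is an illustration under assumed rates.

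**Inputs**
- b, the share of patients with an abnormal baseline ECG: assumed, 10% to 40%.
- i, the rate of new abnormality among patients normal at baseline: assumed, 5% to 20%.
- Pre-existing abnormalities persist: assumed.
- n = 30, the approximate size of a Phase 1b cohort (Protocol Section 4.1.3).

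**Formulas**
- Share counted as abnormal post-baseline: C = b + (1 − b) × i.
- Pre-existing part of that count: b / C.

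Each cell shows C, then the pre-existing part:

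| b | i = 5% | i = 10% | i = 20% |
|---|---|---|---|
| 10% | 14.5%; 69% | 19.0%; 53% | 28.0%; 36% |
| 20% | 24.0%; 83% | 28.0%; 71% | 36.0%; 56% |
| 30% | 33.5%; 90% | 37.0%; 81% | 44.0%; 68% |
| 40% | 43.0%; 93% | 46.0%; 87% | 52.0%; 77% |

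The extremes: 0.10 / 0.28 = 36% and 0.40 / 0.43 = 93%.

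**Counts in a cohort of 30 with i = 10%.** At b = 10% the crude count is 30 × 0.19 = 5.7 patients, of whom 30 × 0.9 × 0.1 = 2.7 are new. At b = 40% it is 13.8 patients, of whom 1.8 are new. With b = 0 both are 3.0.

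**Contrast between two groups of 30 with true new-onset rates of 5% and 25%**
- b = 0: 5% v 25%, a ratio of 5.
- b = 10%: crude 14.5% v 32.5%, a ratio of 2.2.
- b = 40%: crude 43% v 55%, a ratio of 1.3.

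New cases as a share of all patients at b = 40% are 0.6 × 5% = 3% and 0.6 × 25% = 15%. The ratio stays at 5, and the absolute gap is 12 points on either measure. The crude count therefore keeps that gap but sets it on a higher and noisier base. As a yardstick only, since the plan tests nothing, nominal two-sided 5% power falls from 0.59 at b = 0 to 0.37 at b = 10% and 0.15 at b = 40%. Counting new cases among baseline-normal patients (27 and 18 expected per group) gives 0.54 and 0.39.

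**Link to the by-visit display.** The formula describes patients ever abnormal after baseline. It also holds at one visit if i is read as the share of baseline-normal patients abnormal at that visit, provided attendance does not depend on baseline status.

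**The case against.** **The Table 12 display may never be produced.** Protocol 9.4 calls itself a summary and leaves detail to the SAP, and SAP 6.3.5 plans only a listing. This stands: it would be wrong to say that a misleading incidence figure will be reported. It does not remove the point, because the SAP contradicts its own Section 6.3 and a listing is not an incidence.

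**The row is ambiguous.** It could mean abnormalities that arise after baseline. That cannot be excluded. However, SAP 5.4 uses post-baseline simply for measurements taken after first dose, and the plan says so explicitly where it means treatment-induced, as for ADA. An ambiguous row needs the same clarification.

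**Adverse event reporting covers the important cases.** A reader might infer that a drug effect on the ECG would be masked. The documents do not support that. Protocol 8.3.4 requires clinically significant ECG changes to be reported as adverse events, Appendix 2 includes ECG findings that worsen from baseline, and SAP 6.3.1.5 and 6.3.1.6 summarize treatment-emergent events. New abnormalities judged not clinically significant have no such route.

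**Attrition.** A reader might also infer that patients who stop treatment drop out of numerator and denominator. The row gives no denominator rule, and patients who stop for reasons other than consent withdrawal still have ECGs at the 28- and 100-day visits. That inference is not supported.

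**Repeated counting.** In exploration and expansion the only scheduled post-baseline ECGs are at those two visits. This covers up to about 50 + 240 + 30 = 320 of the 408 planned patients, so counting the same abnormality at many visits applies mainly to dose escalation.

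**Entry criteria.** NYHA above Class 2 and uncontrolled or significant heart disorder are excluded. This limits serious cardiac disease at entry but not minor abnormal tracings.

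**Conclusion.** The point holds as a modest, inexpensive improvement. Table 12 has no baseline reference, SAP 6.3.5 has no table, and SAP 6.3 promises one without a method. As the plan stands, neither document gives the number of patients with a new or worsened ECG, although that is what a primary incidence endpoint calls for.

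The effect of the plain reading of Table 12 is an inflated rate and a diluted contrast between dose groups, with pre-existing cases making up about 36% to 93% of those counted over the assumed ranges. That range rests wholly on assumed prevalence, assumed onset and full persistence; if some baseline abnormalities resolve, the pre-existing share is smaller. It would go too far to say that the figure must mostly reflect baseline prevalence: at b = 10% and i = 20%, new cases are 0.18 / 0.28 = 64% of the count. What is lost is mainly sight of new abnormalities judged not clinically significant, and a proper summary of the ECG endpoint itself.

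**What to change.** In SAP 6.3.5, consistent with SAP 6.3, add by dose, cohort and study part:

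1. A shift table from baseline (SAP 5.4) to the worst post-baseline ECG category: normal, abnormal not clinically significant, abnormal clinically significant. Include a row or column for missing, and include unscheduled ECGs in the worst value.
2. The number and percentage of patients with a new or worsened abnormality at any post-baseline ECG, with the denominator stated (for example, patients with a baseline and at least one post-baseline ECG).

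Keep the by-visit frequency as supportive. SAP 5.1 pools escalation and exploration patients at the same dose, but escalation patients have an ECG every cycle, so show the two portions separately as well.

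Align Table 12 at the next protocol amendment. None is needed for this alone: Protocol Section 9.0 requires one only when a principal feature changes, and the SAP is to be finalized before database lock.

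The cost is SAP wording, one shift table and one incidence display. No ECG or visit is added. This assumes that the case report form records the same ECG interpretation categories before and after first dose, which should be confirmed.

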#### 9.4.3 Pharmacokinetic Analyses

The following PK parameters of FPT155 will be summarized.

Endpoint	Statistical Analysis Methods
The following PK parameters will be derived from concentration-time data for FPT155 when appropriate and applicable to characterize single-dose/multiple dose PK. 

• AUC

• <math>C_{max}</math>

• <math>C_{trough}</math>

• CL

• <math>t_{1/2}</math>

• <math>V_{ss}</math>

• <math>C_{max}</math> and <math>C_{trough}</math> as well as the accumulation ratio of <math>C_{max}</math> and <math>C_{trough}</math> for pembrolizumab may be calculated if the data are available

 Other parameters, such as dose proportionality, accumulation ratio, attainment of steady state, will also be estimated if the data are available.	Individual and mean ( $\pm$ SD) serum FPT155 and pembrolizumab concentration-time data will be tabulated and plotted by dose level, respectively. PK parameters of FPT155 and pembrolizumab will be tabulated and summarized by dose level when appropriate and applicable, respectively. The impact of immunogenicity on FPT155 and pembrolizumab exposure will be assessed, tabulated, and summarized by dose level as data allow.
Assessments of time-dependence of PK, the effect of body weight as well as other covariates on PK, and exposure-response relationship for FPT155 will be conducted, when the data allow, to determine the appropriate dosing approach (eg, body weight-based or fixed dosing) for future trials.	The effect of body size on PK and correlation of exposure with clinical outcomes and toxicity will be assessed for FPT155 when data allow. These analyses will be used to determine the appropriate dosing approach (eg, body size-based or fixed dosing) to support the proposed dose and dose regimen(s) for further trials.

#### 9.4.4 Immunogenicity Analyses

Endpoint	Statistical Analysis Methods
Incidence of ADA to FPT155 and pembrolizumab	Frequency distribution of baseline ADA-positive subjects for FPT155 and pembrolizumab and FPT155 and pembrolizumab treatment induced ADA-positive subjects after initiation of the treatment; titer (titer range), respectively. May characterize ADA as either transient or persistent ADA.

#### 9.4.5 Other Analyses

#### 9.5 Interim Analyses

There is no planned interim analysis in this study.

## 10.0 REGULATORY, ETHICAL, AND STUDY OVERSIGHT CONSIDERATIONS

### 10.1 Regulatory and Ethical Considerations

#### 10.1.1 Good Clinical Practice

The procedures set forth in this study protocol are designed to ensure that the Sponsor and investigator abide by all applicable laws, regulations and guidelines, including ICH Good Clinical Practice (GCP) guidelines and international guidelines for ethical practices, including the Declaration of Helsinki (1989) and the Council for International Organizations of Medical Sciences (CIOMS) International Ethical Guidelines.

Before the first patient is screened, the study protocol, including any amendments thereto, the form ICF, the Investigator Brochure and any other relevant documents must be approved by the IRB/IEC, in accordance with applicable laws, regulations and guidelines. The Sponsor, Sponsor's agents, and investigator must ensure that all ethical and legal requirements have been met before the first patient is enrolled in the study.

If a significant safety issue is identified by the Sponsor, either from an individual case report or review of aggregate data, the Sponsor will promptly notify the applicable regulatory authorities and investigators. Investigators will then notify local IRB/IECs as deemed appropriate based on individual IRB/IEC policy. A significant safety issue is one that has a significant impact on the course of the clinical trial or program (including the potential for suspension of the trial program or amendments to protocols) or warrants immediate update of informed consent.

All potential serious breaches must be reported to the Sponsor or designee immediately. A serious breach is a breach of the conditions and principles of GCP in connection with the study or the protocol, which is likely to affect, to a significant degree, the safety or physical or mental integrity of the subjects of the study or the scientific value of the study.

The investigator will also be responsible for providing oversight of the conduct of the study at the site, including oversight of all personnel involved in the study, and adherence to all applicable laws and regulations, as set forth in the Clinical Trial Agreement.

Personnel involved in conducting this study will be qualified by education, training, and experience prior to performing their respective tasks.

The study will not use the services of study personnel against whom sanctions have been invoked or who have engaged in scientific misconduct or fraud (e.g., loss of medical licensure, debarment).

